4.3.1.3. Urine PK Concentrations

Urine samples to determine ELX-02 concentrations in urine will be collected at the following intervals on Day 1 and Day 29:

- Predose and during the following post-dose intervals:
 - hourly during 0-12h (\pm 15 min) time period, (0-1h, 1-2h, 2-3h, 3-4h, 4-5h, 5-6h, 6-7h, 7-8h, 8-9h, 9-10h, 10-11h, and 11-12h)
 - 6-hourly pooled in 12-24h (\pm 15 min) time period, (12-18h and 18-24h)
 - 12-hourly pooled after 24h up to 72h, (24-36h, 36-48h, 48-60h and 48-72h).
- Urine will be pooled in each interval (1, 6 or 12-hour interval), volume measured, and an aliquot will be processed to determine ELX-02 concentration.

4.3.1.4. Urine PK Parameters

The following urinary PK parameters will be calculated:

- Ae: Amount excreted in urine in an interval: 0-1h, 1-2h, 2-3h, 3-4h, 4-5h, 5-6h, 6-7h, 7-8h, 8-9h, 9-10h, 10-11h, 11-12h, 12-18h, 18-24h, 24-36h, 36-48h, 48-60h, and 60-72h on Day 1 and Day 29. Cumulative amount excreted will also be calculated, i.e. Ae_{12h}, Ae_{24h}, Ae_{48h}, Ae_{72h}.
- R_{max}: Maximum amount excreted in urine in a collection interval.
- t_{R_{max}}: Time when maximum amount is excreted in urine. This will be mid-point of the collection interval.
- Fe: Percent of dose excreted in urine on Day 1 and Day 29 (Ae_(t)/dose*100), where t = 12, 24, 48, 72 (will be shown as Fe_{12h}, Fe_{24h}, Fe_{48h}, Fe_{72h}).
- CL_R: Renal clearance on Day 1 and Day 29 (CL_R = Ae_{72h} / plasma AUC_{72h}). If Ae_{72h} or AUC_{72h} is not available, CL_R will be calculated based on data up to 48 hours.

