#### 7.4.2. Urine Collection

Urine samples, to measure the rate of ELX-02 excretion, will be collected at the timepoints specified in Section 7.1 and in Table 1.

- Day 1: Predose collection (first void in the morning). Urine samples for PK, biomarker, and creatinine analysis will be collected. Specific gravity will be calculated for the collection.
- Day 1 (0-12 hours postdose collection period): Subjects will be encouraged to void as frequently as possible (i.e., asked every hour if they can collect urine), and each individual sample will be collected separately. Each sample's weight will be recorded individually prior to removing urine for analyses. Specific gravity will be calculated for each collection.
- Day 1: 12-24 hours postdose collection period. This urine collection period includes all voids starting after 12h and includes the first void on the next day (i.e., 24h postdose void).  
The urine will be collected every 6h (i.e., 12-18h collection and 18-24h collection). The 12-18h voids and the 18-24h voids will be collected into separate urine collection containers.  
In addition, a single urine collection will be taken 24 hours after dosing using a third container (i.e., first morning void of Day 2). All urine containers will be weighed individually and the weights will be recorded. Urine samples for urinalysis, biomarker and creatinine analysis will be withdrawn from the single 24h urine void. Urine samples for PK analysis will be withdrawn from the pooled 12-18h and pooled 18-24h urine collection containers. Specific gravity will be calculated for each collection.
- Day 2 – Day 3: 24-48 hours postdose collection period. This urine collection period includes all voids subsequent to the 24h postdose void and includes the first void on the next day (i.e., 48 hours postdose void).  
The urine will be collected every 12h (i.e. 24-36h collection and 36-48h collection). The 24-36h voids and the 36-48h voids will be collected into separate urine collection containers.  

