After weighing and removing urine for analyses, the collection containers with remaining urine may be discarded.

**If urine cannot be obtained at a certain time interval it will be duly recorded and urine will be collected at the next time interval.**

Urine collection will be timed and measured for weight to determine the retained fraction of ELX-02 concentration and delay of excretion of the retained fraction and the PK.

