4.3.3. Pharmacokinetic Data Reporting

Tables:

All plasma and urinary PK concentrations will be summarized by dose, final diluted injection concentration, day, and timepoint using descriptive statistics (number of subjects, mean, SD, median, coefficient of variance [CV%], minimum and maximum). All PK concentration and descriptive statistic values will be reported to 3 decimal places.

All plasma and urinary PK parameters will be summarized by dose, final diluted injection concentration, and day using descriptive statistics (number of subjects, mean, SD, median, CV%, minimum and maximum, geometric mean, and geometric CV%). All PK parameters and descriptive statistic values will be reported to 3 decimal places, with the exception of the individual t_{max} values, which will be reported to 2 decimal places. Footnotes will include information on parameters not included in summaries and the reasons for not including.

All BLQ, zero, and missing values of PK parameters will not be included in concentration and parameters summary calculations. If the number of non-BLQ, non-zero, and non-missing values are less than 3 in a summarization group, summary statistics will not be calculated.

Listings:

Individual plasma PK sample collection times will be listed by cohort, and will include details about subject number, cohort, dose, day, nominal sample time point, actual sample time point and concentration in the PK population. If any subjects are excluded from the PK population, a separate listing will be produced for these subjects if PK parameters are calculable.

Individual urine PK sample collection times will include details about subject number, cohort, dose, scheduled urine collection interval, actual start and end time of urine collection interval, urine volume collected in the urine collection interval, and concentration in the PK population.

All values will be reported to 3 decimal places, with the exception of the individual t_{max} values,

which will be reported to 2 decimal places.

All BLQ concentrations or missing data will be labeled as such in the concentration data listings.

Figures:

Plasma PK concentration and PK parameter figures:

- Subject profile for plasma concentration-time will be presented graphically on a linear and semi-log scale for the PK population (overlaid Day 1 and Day 29, including C_{0h} and C_{1h} on each scheduled day between Day 1 and Day 29).

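### SAP 4.3.1.4: Rmax is an amount not divided by elapsed time, so missed hourly voids can inflate it and shift tRmax

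*SAP*

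**What the plan says.** SAP 4.3.1.4 defines Rmax as "Maximum amount excreted in urine in a collection interval" and tRmax as "Time when maximum amount is excreted in urine. This will be mid-point of the collection interval".

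SAP 4.3.1.3 lists twelve hourly intervals from 0 to 12 h, then 6 h and 12 h pools: "Urine will be pooled in each interval (1, 6 or 12-hour interval), volume measured".

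Protocol 7.4.2 describes the hourly part less strictly. "Subjects will be encouraged to void as frequently as possible", with an hourly prompt, and each void is kept separately. If no urine can be obtained in an interval, this is recorded and "urine will be collected at the next time interval". SAP 4.3.1.4 gives no rule for the merged interval that results.

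The data needed for a rate are already planned. The urine listing in SAP 4.3.3 includes the scheduled interval and the "actual start and end time of urine collection interval".

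The last collection period is described in three ways. SAP 4.3.1.3 ends its list with "48-60h and 48-72h", SAP 4.3.1.4 uses 48-60 h and 60-72 h, and protocol 7.4.2 draws the PK sample from a single pooled 48-72 h container.

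**The concern.** A maximum over collection intervals is a peak measure only if the intervals last equally long. On paper the first twelve do. In practice the protocol expects that some hourly voids will not happen and sends that urine into the next collection. That collection then holds two or three hours of excretion but competes for the maximum against true one-hour amounts, and it will usually win. Rmax then depends partly on how often the subject voided near the peak, and tRmax on when.

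Both would be summarised by dose, injection concentration and day (SAP 4.3.3). With six ELX-02 subjects per cohort, one subject whose Rmax is doubled raises the cohort arithmetic mean by a factor of (5 + 2)/6 = 1.17, other things equal. A difference between doses, or between Day 1 and Day 29, could therefore be partly a difference in voiding.

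**Working it through.** The plan states no Rmax or tRmax value, so there is no figure of its own to reproduce.

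**Inputs**
- Half-life 2 to 4 h, plasma tmax about 0.5 to 1.0 h, and near-complete urinary recovery in the first 12 h: protocol 1.2.2, Pharmacokinetics.
- Half-life 2 to 8 h: SAP 1.1.1. This is used only in step 4.
- Assumptions: one compartment, first-order absorption, and the whole dose excreted in urine.

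**Step 1: model.** Let k = ln 2 / half-life, and choose ka so that tmax = ln(ka/k)/(ka − k). The fraction of dose excreted by time t is

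F(t) = 1 − [ka·exp(−kt) − k·exp(−ka·t)]/(ka − k).

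The amount in an interval from a to b is F(b) − F(a). Recovery by 12 h comes out at about 98%, 93% and 87% for half-lives of 2, 3 and 4 h, in reasonable agreement with the protocol.

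**Step 2: one case in full (tmax 1.0 h, half-life 3 h).** k = 0.231 and ka = 2.68, so F(1) = 13.8%, F(2) = 31.1% and F(3) = 45.3%.
- Best hour is 1-2 h: 31.1 − 13.8 = 17.3% of dose, mid-point 1.5 h.
- No void at 2 h: 1-3 h is collected together, 45.3 − 13.8 = 31.5%. Rmax is 31.5/17.3 = 1.82 times the best hour. The actual mid-point is 2.0 h, or 2.5 h if the collection keeps the label 2-3 h.
- No void at 1 h or 2 h: 0-3 h is collected together, 45.3%, or 45.3/17.3 = 2.62 times.
- Divided by actual duration: 31.5/2 = 15.7% per hour (0.91 times) and 45.3/3 = 15.1% per hour (0.87 times).

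**Step 3: the full range.** Amounts are % of dose; the multiple of the best hour is in brackets.

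| tmax, half-life | Best hour | One missed: 0-2 h | One missed: 1-3 h | Two missed: 0-3 h | Two missed: 1-4 h |
|---|---|---|---|---|---|
| 0.5 h, 2 h | 25.0 | 47.0 (1.88) | 37.5 (1.50) | 62.5 (2.50) | 48.5 (1.94) |
| 0.5 h, 3 h | 18.0 | 34.9 (1.94) | 30.4 (1.69) | 48.3 (2.69) | 41.0 (2.28) |
| 0.5 h, 4 h | 14.0 | 27.7 (1.98) | 25.2 (1.80) | 39.2 (2.80) | 34.9 (2.49) |
| 1.0 h, 2 h | 22.7 | 40.8 (1.80) | 39.9 (1.76) | 58.0 (2.55) | 52.2 (2.30) |
| 1.0 h, 3 h | 17.3 | 31.1 (1.80) | 31.5 (1.82) | 45.3 (2.62) | 42.8 (2.47) |
| 1.0 h, 4 h | 13.9 | 25.0 (1.80) | 25.8 (1.86) | 36.9 (2.66) | 35.9 (2.58) |

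One missed early void gives 1.50 to 1.98 times the best hour, and two in a row give 1.94 to 2.80 times. In the same cases the maximum rate (amount over actual duration) is 0.80 to 1.00 times its full-schedule value.

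Later misses matter less. Missing only the 3-4 h void changes nothing at a half-life of 2 h. At 3 to 4 h it gives 1.07 to 1.33 times and moves tRmax to 4.0 h.

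**Step 4: do the longer pools set Rmax?** With every hourly void obtained and half-life 2 to 4 h, the maximum is always in 0-1 h or 1-2 h (13.9 to 25.0% of dose). The 12-18 h pool holds 1.4 to 8.6%, 24-36 h at most 1.5%, and 48-72 h at most 0.03%. The 12-18 h pool overtakes the best hour only above a half-life of about 5.1 h, where modelled 12 h recovery has fallen to about 80%. At 8 h the pool holds 14.5 to 14.7% against 7.7%, but recovery is then only 64%. A bi-exponential check, with 5 to 20% of the dose in an 8 h slow phase on top of a 2 to 4 h main phase, kept the maximum at 1-2 h (12.6 to 22.0%, against 2.2 to 9.6% in 12-18 h).

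**The case against.** A reader might infer that the unequal scheduled intervals alone make Rmax and tRmax meaningless, with tRmax landing at 15 h at the longer half-lives in the SAP. The documents do not support that. Under the protocol's kinetics the peak stays among equal one-hour intervals, and complete hourly voiding identifies it correctly. The 15 h result needs the whole dose to leave at a half-life above about 5 h. That is inside the SAP's range but fits poorly with near-complete 12 h recovery, and with the rapid, large elimination phase described in protocol 1.1.2. The 24 h interval belongs to the protocol, not the SAP, and would hold almost no drug.

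Three further points count against the concern:
- **Actual times.** SAP 3.10 says that final PK parameters use actual time from dose. This may already correct the tRmax mid-point, for example to 2.0 h rather than 2.5 h for a 1-3 h collection. It cannot correct Rmax, because that definition contains no time.
- **Frequency.** The documents give no rate of missed voids. Water before dosing, hourly fluids and the hourly prompt should all reduce them. The multiples above are therefore per affected subject, not expected cohort shifts.
- **Importance.** Rmax and tRmax are absent from the protocol's urine parameter list (7.4.4). They have no planned test and do not enter Fe, CL_R or the dose-proportionality model. The SAP also labels Rmax openly as an amount.

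All three stand as limits on the size of the point. None supplies a rule for merged intervals.

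**Conclusion.** The point holds in limited form. Rmax mixes peak excretion with voiding pattern because merged collections compete with one-hour ones. An affected subject's Rmax would be about 1.5 to 2.0 times the best hourly amount after one missed early void, and about 1.9 to 2.8 times after two in a row. tRmax shifts toward the merged interval. These figures rest on the one-compartment model, complete urinary excretion, tmax 0.5 to 1 h and half-life 2 to 4 h. Scheduled interval length is not the driver at those half-lives. The consequence is confined to descriptive urine summaries: no test, dose decision or main PK conclusion in the plan depends on either parameter. This is a minor improvement.

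**What to change.** In SAP 4.3.1.4:
- Define Rmax as the maximum urinary excretion rate, Ae divided by actual interval duration. Duration runs from the end of the previous void (from dosing for the first interval) to the end of the current void.
- Define tRmax as the mid-point of that actual interval.
- Flag intervals that merge one or more missed collections and footnote them in the summaries. The rate still averages over the peak in a merged interval (about 0.8 to 1.0 times the full-schedule value), so dividing by time reduces the problem without removing it.
- Keep interval and cumulative Ae as they are for Fe and CL_R.

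Separately, reconcile the last collection period across SAP 4.3.1.3, SAP 4.3.1.4 and protocol 7.4.2, so that the analysis intervals match the containers actually collected.

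The cost is a few lines of SAP text and a short change to the derivation. The start and end times are already to be listed, so no new data are needed. Check only that the recorded start is the previous void and not the scheduled hour.

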4.3.2. Dose Proportionality Assessment

Differences in PK profiles between final diluted injection concentrations (50 vs 100 mg/mL) will be explored using the figures (Section 4.3.3) and the “by concentration” tables. AUC and C_{max} will be evaluated using the ratio with its 90% confidence interval to compare Cohort 3 vs 5 and Cohort 4 vs 6. The elimination half-life, t_{1/2}, will be evaluated using the Kruskal-Wallis test. If no apparent differences in the PK profiles and PK parameters between the injection concentrations are observed, the PK data from two different cohorts with the same dose will be pooled together for assessing dose proportionality. Otherwise, dose proportionality will be assessed using the data from Cohorts 1, 2, 5, 6, and 7 in which the lower diluted injection concentration (50 mg/mL) was administered.

Dose proportionality will be assessed using a power model separately on Day 1 and Day 29, including the log-transformed PK parameters (C_{max} , AUC_t , and AUC_{inf}) as the dependent variables and the log-transformed dose as the fixed effect. Individual PK values will be used to perform a least-squares linear regression analysis, using the formula:

$\log_{pkvar} = A + \beta \times \log_{dose}$, where:

- ' \log_{pkvar} ' represents the natural log transformed C_{max} , AUC_t , and AUC_{inf} .
- ' \log_{dose} ' represents the natural log transformed dose.

The slope for log-transformed dose (β) will be estimated with its 90% confidence interval to examine dose proportionality. The PROC REG procedure will be used in SAS in the following data step:

```
PROC REG DATA=pkparam alpha=0.10; MODEL log_pkvar = log_dose / CLB; RUN;
```

The t_{max} will be compared between dose groups and days (Days 1 and 29) using the Kruskal-Wallis one-way analysis of variance (ANOVA). P-values based on the Kruskal-Wallis test will be presented.

Additional statistical analysis may be performed. If applicable, steady state will be informally assessed via a visual inspection of the figures of predose and 1-hour postdose plasma concentrations vs time (day).

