3.10. Missing, Unused, and Spurious Data

In general, there will be no substitutions made to accommodate missing data points, other than described in this section. All data recorded on the eCRF will be included in data listings.

When tabulating AE data, partial dates will be handled as follows. If the day of the month is missing, the onset day will be set to the first day of the month unless it is the same month and year as study treatment. In this case, in order to conservatively report the event as treatment-emergent, the onset date will be assumed to be the date of first dose. If the onset day and month are both missing, the day and month will be assumed to be January 1, unless the event occurred in the same year as the study treatment. In this case, the event onset will be coded to the date of first dose in order to conservatively report the event as treatment-emergent. A missing onset date will be coded as the date of first dose. If the resulting onset date is after a reported date of resolution, the onset date will be set equal to the date of resolution. Imputation of partial dates is used only to determine whether an event is treatment-emergent; data listings will present the partial date as recorded in the eCRF.

Missing AE severities will not be imputed and will be considered missing in any tabulations of AE severity. When relation of AE to the study drug is missing, the AE will be considered “related” to study drug.

When tabulating concomitant medications, if an end date is missing or the medication is ongoing at the time of first dose, the medication will be considered concomitant.

All final PK parameters will be calculated based on actual time from dose. Interim PK parameters may be calculated based upon scheduled time if actual time data are not yet available.

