4.3.1. PK Concentrations and Parameters

4.3.1.1. Plasma PK Concentrations

Blood samples to determine ELX-02 concentrations in plasma will be drawn on Day 1 and Day 29 at the following nominal time points:

- Predose, 15 min (\pm 2 min), 30 min (\pm 5 min), 45 min (\pm 5 min), 1h (\pm 5 min), 3h (\pm 15 min), 6h (\pm 15 min), 12h (\pm 30 min), 24h (\pm 1h), 36h (\pm 1h), 48h (\pm 1h), 72h (\pm 1h).

and on Days 4, 8, 11, 15, 18 and 22 at the following nominal timepoints:

- Predose and 1h postdose (\pm 5 min).

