4.3.1.2. Plasma PK Parameters

All final PK parameters will be calculated based on actual time from dose. Interim PK

parameters may be calculated based upon scheduled time if actual time data are not yet available. All values below the lower limit of quantification (BLQ) predose and in the absorption phase prior to the first quantifiable concentration will be substituted by zeros. All BLQ values occurring after the first quantifiable concentration will be treated as missing when calculating PK parameters.

The following plasma PK parameters will be determined for ELX-02, as appropriate, according to the definitions and methods of calculation below:

- C_{\max} : Maximum plasma concentration directly obtained from the experimental data of plasma concentration vs time curves, without interpolation (Day 1 and Day 29).
- t_{\max} : Time corresponding to maximum plasma concentration, directly obtained from the experimental data of plasma concentration vs time curves, without interpolation (Day 1 and Day 29).
- AUC_t : Area under the plasma concentration-time curve calculated from time of administration to the last quantifiable concentration, computed using the linear trapezoidal rule (Day 1 and Day 29).
- AUC_{24h} : Area under the plasma concentration-time curve calculated from time of administration to time 24h, computed using the linear trapezoidal rule (Day 1 and Day 29).
- AUC_{48h} : Area under the plasma concentration-time curve calculated from time of administration to time 48h computed using the linear trapezoidal rule (Day 1 and Day 29).
- AUC_{72h} : Area under the plasma concentration-time curve calculated from time of administration to time 72h, computed using the linear trapezoidal rule (Day 1 and Day 29).
- $\%AUC_{\text{extrap}}$: Percent AUC extrapolated to infinity from last observed non-BLQ concentration.
- AUC_{inf} : The area under the plasma concentration-time curve extrapolated to infinity, calculated as $AUC_t + C_{\text{last}} / \lambda_z$, where C_{last} is the last concentration above the lower limit of quantification (LLOQ) (Day 1 and Day 29). If $\%AUC_{\text{extrap}}$ is greater than 20%, the AUC value will be flagged in TLFs, footnoted, and not included in the calculation of summary statistics.
- C_{0h} : Plasma concentration observed at predose at each dosing
- C_{1h} : Plasma concentration observed at 1h postdose at each dosing.
- C_{last} : Last observed non-BLQ concentration.
- T_{last} : Time from dose when C_{last} occurs.

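### SAP 4.3.2 tests tmax on Day 1 against Day 29 with Kruskal-Wallis, an independent-groups test, although the same subjects supply both values

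*SAP*

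**What the plan says.** In SAP section 4.3.2 one test covers two comparisons: tmax "will be compared between dose groups and days (Days 1 and 29) using the Kruskal-Wallis one-way analysis of variance (ANOVA"). The output is fixed as well: "P-values based on the Kruskal-Wallis test will be presented".

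The two days are repeated measures. SAP 4.3.1.1 states "Blood samples to determine ELX-02 concentrations in plasma will be drawn on Day 1 and Day 29 at the following nominal time points", and SAP 4.3.1.2 defines tmax as "directly obtained from the experimental data of plasma concentration vs time curves, without interpolation (Day 1 and Day 29"). Each subject stays in one cohort and receives nine doses (SAP 1.2.1).

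Protocol 9.2 asks for suitable non-parametric methods for dose groups and days without naming any, so the choice of Kruskal-Wallis for both was made in the SAP. SAP section 5 lists the changes from the protocol and does not mention tmax.

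Two neighbouring statements bear on which data enter the test. For Cmax and AUC, "Dose proportionality will be assessed using a power model separately on Day 1 and Day 29"; the tmax sentence has no such wording. If the two injection concentrations look alike, "the PK data from two different cohorts with the same dose will be pooled together for assessing dose proportionality"; nothing says whether tmax follows that rule.

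**The concern.** Kruskal-Wallis takes its reference distribution from independent groups. With Day 1 and Day 29 as the two groups, every subject appears once in each, and the test ignores the link. Positive correlation between a subject's two values makes the day difference less variable than the test assumes, so the p-value is too large.

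The risk is a missed shift: a non-significant result could be read as evidence that absorption time is stable under repeated dosing. This is also the only between-day test in the SAP, because section 5 removes the day and dose-by-day terms from the power model.

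The stakes are small. Cmax and AUC proportionality, the decisions on escalating dose and the safety analyses do not use this p-value.

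**Working it through.** The documents give no power, alpha, correlation or SD for tmax, so there is no planned figure to reproduce. The size has to come from stated assumptions.

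**Inputs from the documents**
- Six ELX-02 subjects per cohort and seven cohorts (SAP 1.2.1): 7 × 6 = 42. The 50 mg/mL cohorts alone (1, 2, 5, 6, 7): 5 × 6 = 30.
- Nominal sampling times and windows (SAP 4.3.1.1): 15 min ± 2; 30, 45 and 60 min ± 5; 3 h ± 15.
- "All final PK parameters will be calculated based on actual time from dose" (SAP 3.10), so tmax is not confined to the nominal grid.
- Single-dose median tmax of about 0.5 to 1.0 h (Protocol 1.2.2).

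**Assumptions**
- Two-sided 5% level; complete data on both days.
- Log-normal true tmax with median 0.6 h and log SD 0.45; within-subject correlation on the log scale of 0, 0.3, 0.5 or 0.7.
- Each value is read at the nearest actual sampling time, with times uniform within the windows and rounded to the minute.
- Shifts: 22% of 36 min = 7.9 min; 35% of 36 min = 12.6 min; 50% of 36 min = 18 min.

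**Direction, in closed form.** For two means with common variance σ² and correlation ρ, the true variance of the day difference is 2σ²(1 − ρ)/n. An independent-groups test uses 2σ²/n. The nominal z-statistic therefore has SD √(1 − ρ), and the true error is 2[1 − Φ(1.96/√(1 − ρ))]:
- ρ = 0.3: 1.96/0.837 = 2.34, error 1.9%
- ρ = 0.5: 1.96/0.707 = 2.77, error 0.6%
- ρ = 0.7: 1.96/0.548 = 3.58, error 0.03%

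This is a guide only. Rank correlation is a little below ρ, and reading tmax at sampling times weakens it further, so the simulated errors below are somewhat higher.

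**Simulation, day comparison over all doses.** There were 4,000 replicates per setting. The Monte Carlo standard error is √(0.05 × 0.95/4000) = 0.3 points at 5% and 0.8 points at 50%. KW is tie-corrected Kruskal-Wallis; SR is Wilcoxon signed-rank with zero differences dropped.

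| n = 42 | ρ = 0.3 | ρ = 0.5 | ρ = 0.7 |
|---|---|---|---|
| True error, KW | 2.6% | 1.0% | 0.2% |
| True error, SR | 5.2% | 4.9% | 4.7% |
| Power, 22% shift, KW | 43% | 42% | 43% |
| Power, 22% shift, SR | 56% | 66% | 82% |
| Power, 35% shift, KW | 80% | 82% | 88% |
| Power, 35% shift, SR | 88% | 94% | 99% |

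At ρ = 0 and n = 42, error is 5.4% (KW) and 5.0% (SR), and power for the 22% shift is 44% for both.

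For the 50 mg/mL cohorts only (n = 30), at ρ = 0.3/0.5/0.7, KW error is 2.2/1.3/0.2% against 4.7 to 5.1% for SR. Power for the 22% shift is 32/29/27% against 42/50/66%.

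A simpler model with continuous normal values and a 0.5 SD shift (n = 42, 2,000 replicates) agrees. At ρ = 0/0.3/0.5/0.7, KW power is 60/61/62/68% and SR power is 60/75/85/98%.

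**Day comparison within one dose group.** Power for a 50% shift, with exact signed-rank:

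| | ρ = 0 | ρ = 0.3 | ρ = 0.5 | ρ = 0.7 |
|---|---|---|---|---|
| n = 6, KW | 23% | 20% | 19% | 19% |
| n = 6, SR | 12% | 16% | 19% | 24% |
| n = 12, KW | 47% | 46% | 47% | 46% |
| n = 12, SR | 43% | 54% | 65% | 79% |

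At n = 6 the smallest exact two-sided signed-rank p is 2/2⁶ = 0.031 and the next is 4/64 = 0.063. All six differences must therefore be non-zero and point the same way to reach 5%.

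**Dose comparison.** Within one day the cohorts are independent and Kruskal-Wallis holds its level (about 4%). If both days were stacked, so that each subject counted twice, the error would be about 10%, 15% and 20% at ρ = 0.3, 0.5 and 0.7. The SAP does not state that reading, and the surrounding text points to testing each day separately, but the sentence does not exclude it.

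**The case against.** The best defence is that little depends on this p-value. The study has no power basis and no multiplicity control (SAP 3.1, 3.7). The secondary PK objective concerns Cmax and AUC. The error is conservative, so it does not produce false claims of change. A shift would remain visible, because tmax is summarised and plotted by day and each subject's two profiles are overlaid (SAP 4.3.3). SAP 4.3.2 also leaves room for further analyses. All of this is true and limits the weight of the point, but none of it prespecifies a paired test or makes the committed p-value valid.

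A second objection is sharper. The SAP does not say whether days are compared over all doses or within each dose, and its PK tables are by dose. Within a cohort of six the paired test does no better unless correlation is high, and at zero correlation it does worse (12% against 23%). That stands. It is why the pooled paired test should carry the comparison and by-dose results should be descriptive. At n = 12 the paired test is ahead from correlation 0.3 upwards.

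The illustrated pooled shifts, about 8 and 13 minutes, are smaller than the 15-minute spacing of the early samples. Whether such shifts matter is a pharmacological question; they serve here only to compare the tests.

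**Conclusion.** The concern holds. As written, the SAP applies an independent-groups test to paired data and commits to reporting the result. The design makes the data paired whatever the correlation; the correlation only sets the cost.

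Over assumed correlations of 0.3 to 0.7 with all 42 ELX-02 subjects, the nominal 5% test runs at 2.6% down to 0.2%. It gives up 13 to 39 percentage points of power for a 22% shift (56 − 43 = 13; 82 − 43 = 39). At zero correlation nothing is lost. The direction needs only positive correlation; the sizes depend on the assumed SD, shift and correlation, on complete pairs, and on a day comparison pooled over doses.

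The consequence is confined to an exploratory PK comparison, so this is a change worth making rather than a threat to the trial's conclusions. The silence on within-day dose testing and on cohort pooling for tmax is a lesser gap in the same section.

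**What to change.** State four things in SAP 4.3.2:

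1. Dose groups: Kruskal-Wallis on tmax, separately on Day 1 and on Day 29.
2. Day 29 against Day 1: Wilcoxon signed-rank on within-subject differences in ELX-02 subjects with both values, with the Hodges-Lehmann median difference and its 90% confidence interval. State how zero differences and ties are handled.
3. By dose: paired differences reported descriptively (median and range). Any by-dose paired test is optional and labelled exploratory, because n is 6 or 12.
4. Whether tmax follows the pooling rule for Cohorts 3 and 5 and Cohorts 4 and 6, which decides whether items 1 and 2 use 42 or 30 subjects.

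The cost is three or four sentences and one procedure call, on data already collected. There are two drawbacks: subjects missing one day drop out of the paired test, and shifts in opposite directions at different doses could cancel in the pooled test. The by-dose description in item 3 is there to show the second.
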